6.3. Eligibility

Review of study inclusion/exclusion criteria will be done at/after the screening visit (Visit S1), before enrolling the subject into the open-label dose-escalation period at Visit T1 and before either randomizing the subject or enrolling the subject into the additional open-label dosing period at Visit R1/A1. Please note that prior to enrolling the subject into the open-label dose-escalation period, regarding the laboratory values, only the Visit T1 pregnancy test (if applicable and if performed at the site), and the Visit S1 hematology, chemistry, PT, PTT, INR, HbA1c, lipid panel, serology, pregnancy test (if applicable), urinalysis, urine drug screen, 24-hr UFC, and salivary cortisol levels need to be reviewed. The screening blood hormone levels are for baselining purposes and the results do not need to be available prior to enrolling the subject.

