3.3. Study Duration

It is anticipated that the overall duration of the study per subject will range from approximately 16-22 weeks, depending upon the duration (if any) required for wash-out and the duration of follow-up.

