6. Female subjects must be postmenopausal > 2 years OR must have been permanently surgically sterilized (bilateral salpingectomy or tubal occlusion) > 2 years OR male partner(s) has had a vasectomy > 2 years OR must consent to use two permitted medically-acceptable methods of contraception throughout the study during any sexual intercourse with a male partner. Permitted medically-acceptable methods of birth control for this study include oral contraceptives, contraceptive implants, Depo-Provera®, contraceptive patch, vaginal ring, male condom, female condom, spermicide, diaphragm with spermicide, cervical cap with spermicide, contraceptive sponge, or an intrauterine device (IUD); IUDs must have been in place for at least 28 days prior to first dose of study drug.

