11. Alcohol or substance abuse (cocaine, amphetamines and/or opioids) within the year prior to screening
12. Abnormal laboratory values as per the guidelines listed below or any other clinically significant, unexplained laboratory abnormality according to the Investigator:
 - Serum ALT or AST > 3 \times ULN
 - Serum total bilirubin > 1.5 \times ULN
 - Serum creatinine > 1.5 \times ULN
 - Glomerular filtration rate < 60 mL/min/1.73 m²
13. Pregnant, breast-feeding, having conceived within the 6 months prior to screening, or having an intent to become pregnant during the study period
14. QTc > 470 msec on electrocardiogram at screening (subjects with a single QTc > 470 msec may have 2 additional ECGs taken during screening and the QTcs averaged; if the average QTc is > 470 msec then the subject is excluded)
15. Known history of Gilbert's syndrome
16. HIV, hepatitis B, or hepatitis C positivity at screening

17. Any malignancy within the previous 5 years, other than curatively treated basal or squamous cell skin cancer or cervical carcinoma *in situ*
18. Previous exposure to any amount of ATR-101
19. Participation in any study of an investigational drug within 30 days prior to screening
20. Significant psychiatric disease, recent severe physical stress, malnutrition, chronic excessive exercise, or any other medical or psychiatric condition that, in the opinion of the Investigator, is likely to confound the interpretation of the study results or prevent the subject from understanding the requirements of or successfully completing the study

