6.10. Laboratory Tests

Blood, urine and saliva samples for assessments of efficacy, safety and PK will be obtained as shown in the study schedule in [Appendix 1](#). Please see the Laboratory Manual for blood collection volumes. Testing of clinical laboratory samples will be carried out by the central clinical laboratory and will include the tests listed in [Table 3](#). Testing of PK samples will be carried out by the central PK laboratory. Samples may also be assessed for other parameters relevant to steroid metabolism. Subjects need to fast from 10 PM (22:00; water and maintenance medications allowed) the evening prior to Visits S1, R1 and R3/ET. Subjects need to be in a seated position for at least 15 minutes prior to collection of blood hormone levels so that renin and aldosterone levels are stable. For other blood tests, subjects may be seated or supine.

For all female subjects of childbearing potential, a serum pregnancy test will be performed via the central laboratory at screening (Visit S1) and a urine pregnancy test will be performed at the study site (preferred; however, if required by the institution/IRB/EC, a serum or urine sample may be submitted to a laboratory for pregnancy testing instead) at all subsequent study visits.

Abnormal, clinically significant results may be verified to rule out laboratory error. Persistent relevant abnormal values must be followed up until the cause is determined or until they return to the baseline value. Abnormal laboratory findings that are considered clinically significant by the Investigator should be recorded as AEs as appropriate (Section [6.9](#)).

Table 3: List of Clinical Laboratory Tests

Hematology	hematocrit (Hct), hemoglobin (Hgb), platelet count, red blood cell (RBC) count, white blood cell (WBC) count with differential
Chemistry	albumin (ALB), alkaline phosphatase (ALK-P), alanine aminotransferase (ALT; SGPT), aspartate aminotransferase (AST; SGOT), blood urea nitrogen (BUN), calcium (Ca), creatinine (including calculated glomerular filtration rate), glucose, total bilirubin, total protein, electrolytes (magnesium, sodium, potassium, chloride, bicarbonate)
Coagulation	PT, aPTT, INR
Metabolic	insulin, HbA1c, lipid panel (total cholesterol, LDL, HDL, triglycerides)
Hormones	11-DOC, 17-OHP, A, A4, ACTH, cortisol, DHEA, DHEAS, free T, P, renin, SHBG, total T

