7.1. Screening Visit, Visit S1

The screening visit should be conducted within 56 days (8 weeks) prior to enrollment into the open-label dose-escalation period. The date of screening is considered to be the date that the first study-related screening assessment is performed. At screening, appropriate study site personnel should:

- Obtain and document informed consent from the subject prior to any study procedures being performed.
- Assign a study-specific subject number.
- Contact the IVRS/IWRS to register the subject in the study
- Obtain and record medical history, demographic data and prior and current medications.
- Record vital signs, height and weight.
- Perform a complete PE.
- Obtain a 12-lead ECG.
- Collect fasting blood samples for hematology, chemistry, PT, aPTT, INR, insulin, HbA1c, lipid panel, HBsAg, HCV, HIV, hormones (11-DOC, 17-OHP, A, A4, ACTH, cortisol, DHEA, DHEAS, free T, P, renin, SHBG and total T) and serum pregnancy test.
 - Note: Subjects who require wash-out of medications that affect cortisol levels should NOT have their hormone levels drawn at S1. Instead, they should complete the required wash-out and return to the site for hormone levels later during the screening period.
 - All blood hormone collections should be performed between 6-10 AM (06:00-10:00), as close to 8 AM (08:00) as practicable.
 - Subjects need to be in a seated position for at least 15 minutes prior to collection of blood hormone levels so that renin and aldosterone levels are stable.
 - If the subject is not fasting, proceed with the visit but mark the sample collection as being non-fasting.

- Collect a urine sample for urinalysis and urine drug screen.
- Review all assessable inclusion and exclusion criteria.
- Provide instructions to the subject regarding 24-hr urine samples and early morning (30-45 minutes after awakening for the day) and late night (10 PM-12 AM; 22:00-00:00) saliva samples to be collected at home prior to the next visit.
 - During the screening period, subjects must perform two 24-hr urine collections, two early morning saliva collections and two late night saliva collections within 28 days prior to enrollment into the open-label dose-escalation period (Visit T1). The two early morning collections should be done on different days from each other, as should the two late night collections. These samples need to be submitted to the central laboratory for processing in time for results to be reviewed for eligibility prior to enrollment.

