7.2. Open-label Dose-escalation Period

Only subjects who meet all of the inclusion criteria and none of the exclusion criteria should be enrolled and enter the 8-week open-label dose-escalation period. During the open-label dose-escalation period, subjects will take their assigned study drug and undergo assessments to evaluate efficacy, safety, tolerability and PK of study drug. At Visit T1, all subjects will initially be assigned to take ATR-101 250 mg BID. After 2 weeks, at Visit T2, all subjects will be assigned to take the next higher dose of ATR-101, 500 mg BID. After 2 additional weeks, at Visit T3, all subjects will be assigned to take the next higher dose of ATR-101, 1000 mg BID. At any time, the ATR-101 dose may be down-titrated as needed for safety reasons at the discretion of the Investigator.

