7.2.1. Visit T1 (Day 1)

At Visit T1, appropriate study site personnel should:

- Record adverse events and update medications.
- Record vital signs and weight.
- Perform a complete PE.
- Collect a urine sample for urinalysis and, if the subject is a woman of childbearing potential, perform a urine pregnancy test (preferred; or submit a serum or urine sample to a laboratory for pregnancy testing if required by your institution/IRB/EC).
- Review all inclusion and exclusion criteria to confirm that the subject is eligible for the study, including all 24-hr UFC and late night salivary cortisol levels collected within the past 28 days.

- Review the mean of all 24-hr UFC levels obtained within the past 28 days to determine the subject's 24-hr UFC stratum (1.3 to $< 4 \times$ ULN (Stratum I) or 4 to $10 \times$ ULN (Stratum II)).
- Please note that prior to enrolling the subject, regarding the laboratory values, only the Visit T1 pregnancy test (if applicable and if performed at the site), and the Visit S1 hematology, chemistry, PT, PTT, INR, HbA1c, lipid panel, serology, pregnancy test (if applicable), urinalysis, urine drug screen, 24-hr UFC, and salivary cortisol levels, need to be reviewed. The screening blood hormone levels are for baselining purposes and the results do not need to be available prior to the enrolling the subject.
- Contact the IVRS/IWRS to confirm enrollment of the subject into the open-label dose-escalation period and obtain study drug assignment.
- Collect blood samples for hematology, chemistry, hormones (11-DOC, 17-OHP, A, A4, ACTH, cortisol, DHEA, DHEAS, free T, P, renin, SHBG and total T) and PK within 30 minutes prior to administration of study drug.
 - All blood hormone collections should be performed between 6-10 AM (06:00-10:00), as close to 8 AM (08:00) as practicable.
 - Subjects need to be in a seated position for at least 15 minutes prior to collection of blood hormone levels so that renin and aldosterone levels are stable.
- Dispense open-label study drug (ATR-101 250-mg tablets) and instruct the subject on self-administration of study drug orally with food BID.
- Have the subject eat breakfast.
- Ask the subject to self-administer study drug with a nonalcoholic beverage (except grapefruit juice) while at the study site. Record the exact time of study drug administration.
- Collect plasma PK samples 1, 2, 3 and 4 hrs after administration of study drug. Record the exact time of each PK sample collection.

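### The Visit T1 pregnancy result must be reviewed before enrolment only if the test is run on site, so a laboratory-testing site without a same-day result may give the first dose on the screening test alone

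*Protocol*

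**What the plan says.** Section 6.3 of the protocol (Eligibility) names the laboratory results that need review before a subject enters the open-label dose-escalation period: "only the Visit T1 pregnancy test (if applicable and if performed at the site), and the Visit S1 hematology, chemistry", followed by the remaining screening tests. Section 7.2.1 (Visit T1) repeats the rule with the same condition: "only the Visit T1 pregnancy test (if applicable and if performed at the site".

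Section 6.10 describes the testing. Women of childbearing potential have a serum test at the central laboratory at S1. At later visits a urine test at the site is preferred, but "if required by the institution/IRB/EC, a serum or urine sample may be submitted to a laboratory for pregnancy testing instead". Section 7.2.1 and footnote f of Appendix 1 carry the same exception.

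Other provisions bear on the point:

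- Section 7.2: "Only subjects who meet all of the inclusion criteria and none of the exclusion criteria should be enrolled".
- Exclusion 13 in Section 4.2: "Pregnant, breast-feeding, having conceived within the 6 months prior to screening, or having an intent to become pregnant during the study period".
- Inclusion 6 in Section 4.1: a woman to whom none of the listed exceptions applies "must consent to use two permitted medically-acceptable methods of contraception throughout the study during any sexual intercourse with a male partner".
- Section 7.1: "The screening visit should be conducted within 56 days (8 weeks) prior to enrollment into the open-label dose-escalation period".

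**The concern.** The protocol foresees sites where a laboratory must run the T1 pregnancy test. For exactly those sites it takes the T1 result off the list of results needed before enrolment. The sample is still collected, but the rule does not make the first dose depend on what it shows.

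What is at stake is subject safety. A conception between S1 and T1 could come to light only after the woman has taken study drug. Found before enrolment, it would be a screen failure. Found afterwards, it is an exposure in pregnancy, with the reporting and follow-up to the end of pregnancy set out in Section 6.9.5. It also ends in removal from the study, and Section 4.3 does not replace subjects who leave after enrolment.

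**Working it through.** There is no statistical figure to reproduce, so the check is to follow one subject through the text.

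1. **Is the T1 result required at a laboratory-testing site?** Sections 6.3 and 7.2.1 say that only the listed laboratory values need review. The T1 pregnancy test is listed on condition that it was run on site. Where Section 6.10 sends the sample to a laboratory, the condition fails and the result is not on the list.

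2. **Which pregnancy result remains on the list?** Only the S1 serum test.

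3. **Does dosing wait?** Section 7.2.1 places the T1 pregnancy sample, the eligibility review, the IVRS/IWRS enrolment, the dispensing of 250-mg tablets and the first supervised dose at one visit. No section makes enrolment or dosing wait for a pending laboratory result.

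4. **How old can the S1 test be?** Section 7.1 allows S1 up to 8 weeks before enrolment: 8 × 7 = 56 days. The interval is most likely to be long in subjects who need a medication wash-out. For them Section 7.1 defers the hormone draw, but it does not defer the pregnancy test.

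5. **Does other text close the gap?** Section 7.2 and the criteria review in 7.2.1 apply exclusion 13 to everyone. The note that follows in 7.2.1 then says which laboratory results that review needs. A site that doses without the laboratory result has followed the specific instruction.

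6. **How many subjects are affected?** This cannot be derived. The protocol does not give the number of laboratory-only sites, their turnaround time or the number of women of childbearing potential. The count may be zero.

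**The case against.** The strongest reply is that the text is consistent and the risk already well covered. On-site testing is the default. The list of results is a minimum and does not stop an investigator from waiting. Exclusion 13 applies at T1, a serum test was done at S1, contraception is generally required, and testing is repeated at every later study visit. Harm needs several things together: a woman of childbearing potential, a site that must use a laboratory, no same-day result, a conception since S1 despite inclusion 6, and an investigator who does not wait. Even then the T1 sample is already with the laboratory, and the dose is the lowest, 250 mg BID, until T2 on Day 15.

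Most of this stands and sets the severity. It does not remove the point. An investigator may wait but is not told to, and contraception does not replace a test that the protocol itself schedules at T1.

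A reader might infer that the protocol allows a woman known to be pregnant to be enrolled, or that a positive laboratory result already in hand could be ignored. Neither is supported: exclusion 13 and Section 7.2 would bar her. A reader might also take 56 days as the usual age of the S1 test. It is only the upper limit.

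**Conclusion.** The concern holds in a narrow form and is minor. As written, the rule lets a site that must use a laboratory, and has no same-day result, give the first dose with no pregnancy result reviewed later than S1, up to 56 days before. This rests on three readings: the word limiting the list in Sections 6.3 and 7.2.1 means what it says, no other section holds the dose, and some site actually uses the laboratory route without same-day reporting. The first two can be checked in the protocol; the third cannot, so no frequency is claimed.

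A reader might go further and see a general failure of pregnancy screening, or a threat to the trial's results. The protocol supports neither. Sites that test on site must review the T1 result before enrolment, and the point does not touch the endpoints or the analysis.

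**What to change.** In Sections 6.3 and 7.2.1, delete the condition that limits the T1 pregnancy test to tests run on site. State that for every woman of childbearing potential a negative T1 result, from site or laboratory, must be reviewed before enrolment and the first dose. On-site testing stays at T1.

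Only for sites that must use a laboratory and cannot get a same-day result, allow the sample to be taken a few days before T1. The sponsor should choose the number of days, which the protocol does not supply, and write it into 7.2.1 and footnote f of Table 6. It has to be stated expressly because the general windows do not clearly cover it: Section 6.1 gives 2 days either side, while Section 7 and Appendix 1 give only plus 2 days.

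The cost is a small wording change. Nothing changes at sites that test on site, and a same-day laboratory result needs only to be read before enrolment. The few remaining sites need one earlier sample or a delayed first dose. Delay costs more: a return visit, repetition of any pre-dose blood samples already drawn, and a check that the baseline urine and saliva collections still fall within 28 days of enrolment.

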6.4. Medical History

A complete medical history will be obtained at the screening visit (Visit S1). The following systems will be reviewed: head, eyes, ears, nose and throat (HEENT), respiratory, cardiovascular, gastrointestinal/hepatobiliary (specifically, a history of liver dysfunction or the presence of hepatomegaly or splenomegaly), genitourinary/ reproductive, musculoskeletal, neurological, psychiatric, endocrine/metabolic, blood/lymphatic, dermatologic and immunologic. Past surgeries will also be recorded.

6.5. Prior and/or Concomitant Medication Assessments

Prior and concomitant medications that should be recorded include any treatments taken from screening (Visit S1) until the end of the study/end of trial (Visit F1), as well as any radiotherapy for Cushing's syndrome performed at any time prior to screening and any treatments for Cushing's syndrome taken within the year prior to screening. Any treatments given during the study other than ATR-101, including blood transfusions, parenteral fluids and herbal preparations, are considered to be concomitant therapies and must be recorded on the eCRF.

6.6. Vital Signs, Height, Weight and Body Mass Index

Vital signs (temperature, systolic and diastolic blood pressure, pulse and respiratory rate) and weight will be measured at each study visit.

Systolic and diastolic blood pressure should be taken in the same arm per subject at each study visit after the subject has been sitting for at least 5 minutes. Any clinically necessary deviations to this will be documented but do not need to be confirmed with the Medical Monitor prior to occurrence or documented as a protocol deviation.

Body weight will be obtained at each study visit, using a calibrated scale, after voiding and without shoes or outerwear (i.e., coats). Height will be assessed only at screening. Body mass index will be calculated based on body weight and screening height.

6.7. Physical Examination

A complete PE will be obtained at Visits S1, T1, R1/A1, and R3/A3/ET. A brief PE will be performed at Visits T2, T3, R2/A2, and F1 (if the subject has their follow-up visit at the study site), with particular attention to assessing the subjects for adrenal insufficiency. At all other visits, targeted PEs may be performed if needed based on adverse events and positives from review of systems.

The following systems will be examined for a complete PE: HEENT, respiratory, cardiovascular, gastrointestinal/hepatobiliary (specifically the presence of hepatomegaly or splenomegaly will be assessed), musculoskeletal, neurological and dermatologic. On a brief PE, the following systems will be examined: respiratory, cardiovascular, gastrointestinal/hepatobiliary and any areas pertinent to any adverse events and positives from review of systems.

6.8. Electrocardiography and Determination of QTc

All subjects will have 12-lead ECGs performed at Visits S1, R1/A1, and R3/A3/ET prior to study drug dosing (if applicable). The ECG test tracings will be interpreted by usual clinic

procedures and ECG findings will be recorded on the eCRF. ECGs will be stored for later analysis if needed.

If the QTc is greater than 470 msec on the screening (Visit S1) ECG, three consecutive ECGs will be obtained and the QTc values corrected by the Fridericia method will be averaged. If the average is greater than 470 msec, the subject will be ineligible for the study.

For all ECGs, the QT interval will be corrected using the Fridericia method ($QTcF = QT/RR^{0.33}$). During the study, if the QTcF is greater than 470 msec, a repeat 12-lead ECG will be obtained as soon as practicable.

In the event of an abnormal ECG (especially in the setting of an intraventricular conduction delay) that makes QTc determination unreliable by standard means, the QT interval will be corrected by the method of Rautaharju et al.¹³

6.9. Adverse Events, Serious Adverse Events and Reporting

6.9.1. Definition of Adverse Event, Adverse Drug Reaction and Unexpected Adverse Drug Reaction

Adverse Event (AE): Any untoward medical occurrence associated with the use of a drug in humans, whether or not considered drug-related.

- All AEs, regardless of relationship to study drug, should be collected beginning from the time the subject signs the study consent until the last study visit or 30 days after the last dose of study drug, whichever is later. (Any SAE judged by the Investigator to be related to the study treatment should be reported to the Sponsor regardless of the length of time that has passed since study completion.) AEs in study subjects include any change in the subject's condition. This includes symptoms, physical findings, or clinical syndromes.
- Wherever possible, a specific disease or syndrome, rather than individual associated signs and symptoms should be identified by the Investigator and recorded. However, if an observed or reported sign or symptom is not considered a component of a specific disease or syndrome by the Investigator, it should be recorded as a separate AE. Additionally, the condition that led to a medical or surgical procedure (e.g., surgery, endoscopy, tooth extraction, or transfusion) should be recorded as an AE, not the procedure. Any medical condition already present at screening should not be reported as an AE unless the medical condition or signs or symptoms present at baseline worsens in severity or seriousness at any time during the study. Clinically significant examination (e.g. electrocardiogram) findings that are detected during the study or are present at screening and worsen during the study should be reported as an AE.
- An abnormal laboratory value may be considered an AE if the identified laboratory abnormality leads to any type of intervention, whether prescribed in the protocol or not. It is up to the Investigator to determine whether an abnormal laboratory value constitutes an AE. If an abnormal laboratory value is caused by a disease process, the disease process and not the laboratory abnormality should be listed as the AE (e.g., if new onset viral hepatitis is causing elevated ALT, hepatitis and not the elevated ALT should be listed as the AE).

- Examples of laboratory abnormalities that should be considered AEs include those that result in withdrawal of the study treatment, withholding study treatment pending some investigational outcome, or additional concomitant treatment. All laboratory abnormalities considered to constitute an AE should be recorded on the appropriate AE page of the eCRF. Laboratory abnormalities do not need to be listed as separate AEs if they are considered to be part of a clinical syndrome that is being reported as an AE. It is the responsibility of the Investigator to review all safety laboratory findings in all subjects. Abnormal values should be commented upon as to clinical relevance or importance on the eCRF or the laboratory report as appropriate. Medical and scientific judgment should be exercised in deciding whether an isolated laboratory abnormality should be classified as an AE.
- Every effort must be made by the Investigator to categorize each AE according to its severity and its relationship to study drug.
- Subjects who develop toxicity on study will be followed until the event resolves, stabilizes or returns to baseline.

Adverse Reaction: All noxious and unintended responses to study drug at any dose should be considered to be adverse reactions. “Responses to study drug” means that there is a causal relationship between the study drug and the responses. “Suspected adverse reaction” implies a lesser degree of certainty about causality than “adverse reaction.”

Unexpected Adverse Reaction: An unexpected adverse reaction is defined as an adverse reaction, the nature or severity of which is not consistent with the applicable product information. For the study drug, the reference safety information is included in the version of the Investigator's Brochure currently in force. The reference safety information will be reviewed yearly and the periodicity of the review will be harmonized with the reporting period of the Development Safety Update Report.

